3.3.2. Assessment Phase

[figure not shown]
The Assessment Phase is the main part of the Physician Survey. In addition to the TROBALT prescribers, the Assessment Phase will include up to 200 respondents from the Screening Phase who have not prescribed TROBALT in order to evaluate the general awareness to the risks associated with TROBALT. The Assessment Phase will evaluate each physician's understanding of specific risks associated with TROBALT use.

The outcome of this study is the proportion of the physicians/epilepsy specialists that correctly respond to individual survey questions. The proportion responding correctly will be tabulated separately for each item.

Physician demographic information will be collected in order to further characterise the respondent population. This will include country, type of medical practice, and number of patients with epilepsy treated. The country in which practice occurs will be collected at the beginning of the survey in order to ensure a sample of respondents from each included country.

At the conclusion of the online survey, the final computer screen will display a summary of the relevant sections from the country-specific Prescribing Information to allow the physician access to the full TROBALT label, to ensure they have a reminder and full understanding of the safety revisions that were implemented in 2013.

^{*} In case of a very low response, known prescribers will be specifically invited to participate. Such enrichment of the sample is not anticipated to bias the outcomes as the targeted physicians will also be DHCP recipients and will need to fulfil inclusion criteria.

3.4. Study Population

3.4.1. Physicians Prescribing Anti-Epileptic Drugs

This survey aims to recruit a random sample of 1000 physicians prescribing AEDs and who have been sent a DHCP letter in Austria, Belgium, Bulgaria, France, Hong Kong, Italy, Norway, Poland, Slovakia, Spain, Switzerland and the United Kingdom.

The selected countries are the eight largest markets in the EU for TROBALT use based on estimated number of patients receiving TROBALT (the United Kingdom, Spain, France, Italy, Belgium, Slovakia, Poland and Austria). One additional EU country (Bulgaria) was selected upon the potential uncertainty related to reimbursement of an ophthalmology exam mandated by the TROBALT PI. Three non-EU countries (Hong Kong, Norway and Switzerland) were selected to represent markets where TROBALT is available, outside the EU.

If required, additional countries may be included in the survey to reach the minimum recruitment target. The recruitment will be from among those who have prescribed an anti-epileptic drug at least once in the last 6 months, and who were on the list to which a DHCP letter was distributed in June 2013. The survey will aim to recruit at least 200 physicians (from the 12 specified countries) prescribing TROBALT for sub-analyses, as these individuals would be expected to be more aware of the risks of TROBALT, and up to 200 physicians not prescribing TROBALT as a comparison.

3.4.2. Inclusion criteria for Physician Survey

Physicians will be required to meet all the following inclusion criteria:

- 1. Must manage patients with epilepsy.
- 2. Must have prescribed an AED at least once in the last 6 months.
- 3. Must be on the list to which a DHCP letter was distributed in June 2013.

3.4.3. Exclusion criteria for Physician Survey

Physicians meeting any of the following criteria will not be eligible to take the survey:

1. Currently an employee of GSK or UBC.

3.4.4. Methods of Recruitment

The physicians will be recruited through an invitation to participate in the survey. The invitation will direct the physicians to the survey website to complete the survey. Invitations will be sent by e-mail to those physicians for whom an e-mail address is available. For those physicians without e-mail addresses, invitations will be sent by mail. If there is no response after the first invitation, then subsequent reminders will be sent until the target of completed surveys is met. During this time, the response rates for each country will be monitored to ensure that the outreach is sufficient to meet target goals.

Physicians will be provided a unique code in the survey invitation letter and will be asked to provide the unique code to gain access to the online survey or when calling the Survey Coordinating Center. The code will be deactivated after use to minimize the possibility for fraud.

Physicians will be paid the equivalent of £60 for their participation, which is fair market value for a survey estimated to take 20 minutes to complete.

3.5. Survey Design

The final study design is based on experience from risk management studies previously completed by GSK and UBC. GSK conducted a similar survey of TROBALT prescribers in 2012 and 2013. Both UBC and GSK have conducted similar knowledge, attitude and behaviour surveys in the US to evaluate Risk Evaluation and Mitigation Strategies (REMS).

3.5.1. Questionnaire Structure

Survey will be composed of multiple choice and close-ended questions. There will be no open-ended questions included. For statements or questions that use "yes" vs. "I don't know" or "no" response options, the desired response for key risk messages is generally "yes" indicating knowledge of, or behaviour in accordance with, the objectives of the program.

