3.5.2. Measures to Minimise Bias in the Surveys

The following are measures to minimise bias in the surveys:

- 1. All questions will be programmed to ensure that questions are asked in the appropriate sequence. Skip patterns will be clearly indicated. Respondents cannot go back to a question once the question has been answered and cannot skip ahead. All questions must be answered in order to complete the survey.
- 2. Response options presented in a list will be randomized to minimize positional bias.
- 3. Comprehension Testing will be conducted among 16 physicians in the UK to evaluate the draft survey questions and to assess the questions understanding and whether proper wording has been used prior to the survey being implemented to the full sample.

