6.2. Analyses

The primary outcome is the proportion of physicians answering each question of the understanding of the risks associated with TROBALT correctly. Point estimates for the proportion with correct responses, and associated confidence intervals, will be calculated for each question about the risks of TROBALT. In the case of multiple choice questions, the number and proportion of physicians reporting each response will also be provided.

The proportion of correct answers to survey questions will be summarised overall, and separately for those physicians who have prescribed TROBALT.

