7. PRECISION BY SAMPLE SIZE

Table 1 summarises the margin of error at the 95% confidence level provided by varying sample sizes and estimates of percentage of physicians indicating a correct response. For example, if the estimate of the percentage of physicians indicating a correct response to an individual survey question is 60%, then a sample of 200 physicians will provide a margin of error of \pm 7.0 percentage points of this estimate with a 95% confidence interval.

Sample Size	Proportion of Correct Responses to Each Question							
	50	60	70	75	80	85	90	
	Precision/ Margin of Error (±%) with 95% Confidence Interval							
50	14	14	12	11	10	9.0	8.0	
100	10	10	9.0	8.0	8.0	7.0	6.0	
150	8.0	8.0	7.3	7.0	6.7	5.7	4.7	
200	7.0	7.0	6.5	6.0	5.5	5.0	4.0	
250	6.0	6.0	5.6	5.4	4.8	4.6	3.6	
300	5.7	5.7	5.3	5.0	4.7	4.0	3.3	
350	5.1	5.1	4.9	4.4	4.3	3.9	3.1	
400	5.0	4.8	4.5	4.3	4.0	3.5	3.0	
450	4.7	4.4	4.2	3.9	3.8	3.2	2.7	
500	4.4	4.2	4.0	3.8	3.6	3.2	2.6	

Table 1 Sample size and precision estimates

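### Risk questions generally keyed to yes, with no stated counterbalance, can score agreement as knowledge and bias the proportion correct upward on those items

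*Protocol*

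**What the plan says.** Section 3.5.1 of the protocol describes a fully closed questionnaire: "There will be no open-ended questions included". For items answered yes, no or I don't know, it adds that "the desired response for key risk messages is generally" yes. Section 4.2 lists the five risks to be asked about, and all of them are presented as genuine risks of the product.

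Section 3.5.2 gives three measures against bias:

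- a programmed question sequence with no going back, in which "All questions must be answered in order to complete the survey";
- option order: "Response options presented in a list will be randomized to minimize positional bias";
- comprehension testing of the wording in 16 UK physicians.

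Section 6.2 defines the endpoint: "The primary outcome is the proportion of physicians answering each question of the understanding of the risks associated with TROBALT correctly". It is reported without adjustment: "Point estimates for the proportion with correct responses, and associated confidence intervals, will be calculated for each question about the risks of TROBALT". Section 8 discusses self-selection, non-response, enrichment, list coverage and pooling of countries. It does not mention agreement bias.

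**The concern.** When an item names a true risk and the credited answer is yes, the wording of the item suggests the answer. A respondent who does not know the risk but is inclined to agree is counted with those who do know it. Where no item of the same kind has no as the correct answer, the two cannot be told apart in the data.

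The error runs in one direction, towards adequate understanding. Sampling error does not include it, so the confidence interval does not cover it and a larger sample does not reduce it. According to the protocol summary and section 1, the results will inform the sponsor's view on whether further risk-minimisation measures are needed. Overstated awareness would favour the answer that they are not.

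**Working it through.** **Inputs from the protocol.** Keying generally to yes and three response options (3.5.1); raw proportion correct per question (6.2); for a sample of 200 and 60% correct, a 95% margin of ±7.0 points (section 7 and Table 1).

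**Assumed input.** g, the share of physicians without the knowledge who still answer yes. The documents give no value. The range used is 10% to 50%; uniform guessing over three options would give 1/3.

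**Step 1: reproduce the protocol's margin.** The simple normal form is 1.96 × √(0.60 × 0.40 / 200) = 6.79 points. With continuity correction it is 6.79 + 100/(2 × 200) = 7.04. The exact (Clopper-Pearson) interval is 52.9% to 66.8%, a half-width of 7.00. The stated ±7.0 is confirmed and is not in dispute.

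**Step 2: bias on a yes-keyed item.** Suppose that all who know the risk answer yes, and let k be their share. Then

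observed = k + (1 − k)g, and bias = (1 − k)g.

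This cannot be negative. In percentage points:

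| True k | g = 10% | g = 20% | g = 1/3 | g = 50% |
|---|---|---|---|---|
| 40% | +6.0 | +12.0 | +20.0 | +30.0 |
| 60% | +4.0 | +8.0 | +13.3 | +20.0 |
| 80% | +2.0 | +4.0 | +6.7 | +10.0 |

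**Step 3: compare with the margin.** At k = 60% the bias equals the margin when 0.40 × g = 0.07, so g = 0.175. With 400 respondents, Table 1 gives ±4.8 points at 60% correct, and the crossing point falls to 0.048 / 0.40 = 0.12. More respondents narrow the interval around the same biased value.

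**Step 4: read it backwards.** If 60% are observed correct, true knowledge is (0.60 − g)/(1 − g): 55.6% at g = 10%, 50.0% at 20%, 40.0% at 1/3 and 20.0% at 50%. Without an estimate of g, the observed figure does not distinguish between these.

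**Step 5: do the listed measures act on g?** Changing the order of options changes where yes appears, not whether an agreeable respondent picks it. Fixed sequence and compulsory answers control navigation and missing data. Comprehension testing checks whether a question is understood, and a perfectly understood question can still invite agreement. None of the three supplies items from which g could be estimated.

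**The case against.** The strongest reply is that the text supports less than a reader might infer from it. Much of this stands.

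- A reader might infer that every primary estimate is affected, or that answering yes throughout earns nearly full marks. The documents do not support this. Section 3.5.1 also provides for multiple-choice questions, its keying remark covers only key risk messages on yes/no-type items, and *generally* leaves room for no-keyed items. A foil is not a key risk message, so the sentence does not exclude foils. The instrument (Appendix 3) is not in the text at hand, so the mix cannot be checked.
- A reader might infer that yes-keying rewards guessing. Uniform guessing over three options scores about 1/3 whichever answer is keyed. That part comes from the closed format. The keying matters for agreement only.
- A reader might think compulsory answering makes it worse. The I don't know option offers an honest exit, which lowers g. It does not stop a respondent who leans towards yes.
- A reader might infer that the difference between prescribers and non-prescribers must shrink. With equal g in both groups it shrinks by the factor (1 − g). If prescribers agree more readily, it could widen. The documents do not settle which.
- The size rests on assumed values. At k = 80% and g = 20% the bias is 4 points, inside the ±5.5 points that Table 1 gives for 80% correct and 200 physicians.

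Reporting details may also properly sit in a statistical analysis plan that is not shown. The missing items themselves are different: no analysis plan can recover foils that were never asked.

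**Conclusion.** The concern holds for the yes-keyed items. The protocol states the keying, the resulting bias can only be upward, no listed measure counters it, and section 8 does not acknowledge it. For g between 10% and 50% the bias is +4 to +20 points at k = 60% and +2 to +10 points at k = 80%. At k = 60% it passes the ±7-point margin once g exceeds about 17.5%.

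This rests on two assumptions: that physicians who know a risk answer yes, and the range chosen for g, for which the documents offer no evidence. The number of affected items is unknown. The conclusion is therefore that the design leaves an unmeasured upward bias on an unknown share of the primary estimates, not that the survey as a whole is invalid. It should be corrected before fielding, because afterwards it can be neither removed nor estimated.

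**What to change.** - **Section 3.5.1:** replace the generally-yes keying with a requirement that each yes/no block contain plausible items for which no is correct (risks or statements not in the TROBALT label), in random order with the true ones. Align the sequencing rule in 3.5.2 with this. Try the foils in comprehension testing; section 3.2 already provides for revising the instrument before the main survey and for translating it later.
- **Section 6.2:** report the yes-rate on the foils by prescriber group, beside the true-risk items. Any correction of the form (observed − g)/(1 − g), with g taken from the foils, should be a sensitivity analysis only. Its assumption should be stated: that physicians without the knowledge say yes equally often to foils and to true items.
- **Section 8:** name agreement bias as a limitation.

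The cost is a few extra closed questions, with their translation, in a survey estimated at 20 minutes (section 3.4.4), and possibly less favourable headline percentages. The closing screen that summarises the prescribing information (sections 3.3.2 and 4.2) already limits the risk that a foil leaves a false impression.

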3.5.2. Measures to Minimise Bias in the Surveys

The following are measures to minimise bias in the surveys:

- 1. All questions will be programmed to ensure that questions are asked in the appropriate sequence. Skip patterns will be clearly indicated. Respondents cannot go back to a question once the question has been answered and cannot skip ahead. All questions must be answered in order to complete the survey.
- 2. Response options presented in a list will be randomized to minimize positional bias.
- 3. Comprehension Testing will be conducted among 16 physicians in the UK to evaluate the draft survey questions and to assess the questions understanding and whether proper wording has been used prior to the survey being implemented to the full sample.

4. STUDY ASSESSMENTS AND PROCEDURES

4.1. Physicians Screening and Assessment

The physicians' introduction information is outlined in Appendix 2, and the survey instrument for the prescribers' assessment is in Appendix 3. The prescribers' questionnaire will begin with a screening module with questions to confirm eligibility. Depending on the answers to the screening questions, survey participation could either be terminated or continued. If ineligible, the respondent is immediately notified with a "thank you" message that survey participation has ended. If eligible, the respondent is allowed to continue survey participation.

The screening questions included in the prescriber survey cover the following general areas:

- 1. Exclusion of employees at GSK or UBC
- 2. Agreement to take the survey
- 3. Time since the last prescription written for any AED
- 4. Ever prescribed TROBALT*
- 5. Currently have patients who are taking TROBALT*
- 6. The last time a patient was initiated on TROBALT*

4.2. Physicians Outcomes

Physicians understanding of specific risks and the appropriate patient population related to TROBALT will be assessed using a standardised questionnaire.

The outcome of this study is the proportion of physicians that correctly respond to individual survey questions concerning risks associated with TROBALT. The proportion responding correctly will be tabulated separately for each item in the physician understanding survey instrument. The risks that will be evaluated in the survey are listed below:

- 1. Pigment changes (discolouration) of ocular tissues, including the retina
- 2. Pigment changes (discolouration) of the nails, lips and/or skin
- 3. Urinary retention (generally within the first 8 weeks of treatment)
- 4. Psychotic disorders (including confusional state and hallucinations)

^{*}Used to ensure that the sample includes at least 200 TROBALT prescribers

5. QTc prolongation.

Physician demographic information will be collected in order to further characterise the respondent population. This will include country, type of medical practice, and number of patients with epilepsy treated.

At the conclusion of the online survey, the final computer screen will display a summary of the relevant information from the country-specific Prescribing Information, which can be printed for reference to allow the physician access to the full TROBALT label to ensure they have a reminder and full understanding of the safety revisions that were implemented in 2013.

5. DATA COLLECTION AND MANAGEMENT

All data collected during the survey will be held confidential. The EDC system used for data collection encrypts all identifiable information, and respondent identifiers are stored separately from the survey responses.

6. DATA ANALYSIS

6.1. Analysis Population

The population for analysis will comprise all physicians recruited into the study, meeting eligibility criteria as assessed in the survey screener, and completing the survey.

The outcomes will be summarised for all 12 specified countries combined.

The two sub-populations for analyses will be 1) the physicians who have prescribed TROBALT after receiving a DHCP letter in June 2013, and 2) the physicians who have prescribed TROBALT in the past, but before receipt of the DHCP letter or the physicians who have never prescribed TROBALT.

6.2. Analyses

The primary outcome is the proportion of physicians answering each question of the understanding of the risks associated with TROBALT correctly. Point estimates for the proportion with correct responses, and associated confidence intervals, will be calculated for each question about the risks of TROBALT. In the case of multiple choice questions, the number and proportion of physicians reporting each response will also be provided.

The proportion of correct answers to survey questions will be summarised overall, and separately for those physicians who have prescribed TROBALT.

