3.3.1. Screening Phase

The Screening Phase seeks to survey physicians to identify the proportion of physicians who have prescribed TROBALT and to summarize the type of medical specialty of those physicians with experience in prescribing TROBALT.

Up to 1000 physicians will be invited to take part, by selecting a random sample of prescribers of AEDs from those who were sent a DHCP letter. Assuming a recruitment failure of 60%, this will permit a target sample of 200 prescribers and 200 non-prescribers to be achieved.

The survey will be composed of multiple choice and close-ended questions. There will be no open-ended questions included.

The electronic data capture (EDC) system will be configured to allow those physicians identified by their responses to the survey in the Screening Phase (Part 1) to transition into the Assessment Phase (Part 2). The EDC system will allow the first 200 physicians who indicate they have prescribed TROBALT since July 2013 to continue to Part 2 and will also limit to 200 the number of non-prescribers who are asked to complete the additional questions in Part 2.

[figure not shown]

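### The pooled overall proportion correct takes its prescriber mix from the recruitment caps and possible enrichment, so unweighted it does not estimate awareness among letter recipients, and the no-bias statement does not hold for it

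*Protocol*

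**What the plan says.** Physicians are recruited at random from the letter list: "Up to 1000 physicians will be invited to take part, by selecting a random sample of prescribers of AEDs" who were sent the letter (Section 3.3.1). Entry to the Assessment Phase is then controlled by group. "The EDC system will allow the first 200 physicians who indicate they have prescribed TROBALT since July 2013 to continue to Part 2", and the system "will also limit to 200 the number of non-prescribers who are asked to complete the additional questions in Part 2". The planning figure is: "Assuming a recruitment failure of 60%, this will permit a target sample of 200 prescribers and 200 non-prescribers to be achieved".

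If response is very low, known TROBALT prescribers will be invited specifically. The footnote in Section 3.3.2 and Section 8 both say that no bias is expected from this, because these physicians also received the letter and must meet the inclusion criteria.

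Section 3.4.1 gives the reason for recruiting prescribers in number: "as these individuals would be expected to be more aware of the risks of TROBALT".

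For the analysis, Section 6.1 states: "The population for analysis will comprise all physicians recruited into the study, meeting eligibility criteria as assessed in the survey screener, and completing the survey". It also says: "The outcomes will be summarised for all 12 specified countries combined". Section 6.2 then states: "The proportion of correct answers to survey questions will be summarised overall, and separately for those physicians who have prescribed TROBALT", with confidence intervals for each question. Neither section mentions weights or limits how the overall figure may be read.

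**The concern.** A physician's chance of entering the Assessment Phase depends on prescriber status, and the protocol itself expects that status to be related to the outcome. A simple proportion over all completers then estimates awareness in whatever mix the caps and the enrichment produce. It does not estimate awareness among letter recipients, the population that Section 8 says the invited sample represents.

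The protocol gives meeting the inclusion criteria as the reason why enrichment is harmless. Eligibility makes each added physician a valid respondent. It does not make the mix representative. Adding known prescribers raises their share and, on the expectation in Section 3.4.1, raises the overall proportion correct.

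The results are to inform whether additional risk-minimisation measures are needed, so an overall figure tilted towards the better-informed group errs in the reassuring direction.

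**Working it through.** **Inputs from the protocol.** Up to 1000 random invitations, 60% recruitment failure, at most 200 prescribers and at most 200 non-prescribers (Section 3.3.1).

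**Inputs assumed.** The prescriber share W among letter recipients and the proportions correct p1 (prescribers) and p0 (non-prescribers) are not given, so ranges are shown.

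**The plan's own figures.** Invitations: 400 / (1 − 0.60) = 1000, as stated. Margin at n = 200 and 60% correct: 1.96 × √(0.6 × 0.4 / 200) = 6.8 points by the simple formula and 7.0 by the exact interval. The stated 7.0 is reproduced.

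**General formula.** Let s be the prescriber share among completers.
- Pooled figure: s·p1 + (1 − s)·p0
- Letter-recipient value: W·p1 + (1 − W)·p0
- Bias = (s − W) × (p1 − p0)

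**Case A: both quotas filled (s = 0.5).**

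| Gap p1 − p0 | W = 10% | W = 20% | W = 30% | W = 50% |
|---|---|---|---|---|
| 10 points | +4 | +3 | +2 | 0 |
| 20 points | +8 | +6 | +4 | 0 |
| 30 points | +12 | +9 | +6 | 0 |

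Example at 80% v 60% and W = 10%: pooled (80 + 60)/2 = 70%; letter recipients 0.1 × 80 + 0.9 × 60 = 62%; bias +8. The simple margin at n = 400 and 70% is ±4.5.

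**Case B: 400 random respondents, caps only, no enrichment.** For W below 50% only the non-prescriber cap binds.

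| W | Prescribers : non-prescribers | s | Bias, 20-point gap | Bias, 30-point gap |
|---|---|---|---|---|
| 10% | 40 : 200 | 16.7% | +1.3 | +2.0 |
| 20% | 80 : 200 | 28.6% | +1.7 | +2.6 |
| 30% | 120 : 200 | 37.5% | +1.5 | +2.3 |

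**What separates the cases.** From 400 random respondents, 200:200 arises without help only at W = 50%. At W = 10%, filling the prescriber quota by random invitation alone would take 200 / (0.40 × 0.10) = 5000 invitations. At a low share, Case A therefore needs enrichment or far more outreach.

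**Margin of a weighted estimate.** With 200:200, 80% v 50% correct and W = 10%: 1.96 × √(0.1² × 0.8 × 0.2 / 200 + 0.9² × 0.5 × 0.5 / 200) = ±6.3 points. A simple sample of 400 at the pooled 65% gives 1.96 × √(0.65 × 0.35 / 400) = ±4.7.

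**The case against.** A reader might infer that the design forces prescribers to be half the sample whatever their true share, so that a bias such as the +12 in Case A is to be expected. The documents do not support this. The 200s are caps and targets: the Protocol Summary speaks of approximately 200 prescribers and up to 200 non-prescribers. On the protocol's own recruitment figures without enrichment, Case B applies and the distortion is small. At W = 10%, a 20-point gap and 240 completers, the pooled figure is (32 + 120)/240 = 63.3%, with a margin of about ±6.1 against a bias of 1.3.

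A reader might also infer that the overall figure is the headline on which the sponsor's decision turns, or that its interval would be read from the n = 400 row of Table 1. Nothing says so. Section 2 concerns prescribers' awareness, Section 6.1 defines both sub-populations, the Protocol Summary plans a comparison between them, and Section 6.2 says intervals will be calculated. Table 1 is a general grid whose worked example uses n = 200.

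Section 6.2 does not call the overall proportion unweighted, and an analysis plan that is not shown could add weights. The remark in Section 8 on low prescriber numbers is made per country, to justify combining countries, and does not fix W. Differences between countries are acknowledged there.

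All of this stands and limits the point. It does not rescue the no-bias statement, which the protocol makes itself, without any reference to weighting, for outcomes that include the overall summary.

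**Conclusion.** The point holds in conditional form. An unweighted overall proportion is biased upward for letter recipients whenever prescribers are over-represented among completers and know more, as Section 3.4.1 expects. The bias can exceed the sampling margin when both quotas fill at a low prescriber share, which is the situation enrichment would create. It is 1 to 2 points at a 20-point gap (2 to 3 at 30 points) with 400 random respondents and caps alone, and zero if prescribers are half of recipients or the groups answer equally well. All sizes rest on assumed W and assumed proportions correct.

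The no-bias statement is wrong for an unweighted overall figure. The separate prescriber estimate is not affected by the pooling.

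**What to change.** - **Section 6.2:** report prescribers and non-prescribers separately as the main results. Either drop the pooled figure or compute it as W·p1 + (1 − W)·p0 with a stratified variance.
- **Source of W:** use Screening Phase respondents from the random invitation only. Section 3.3.1 already sets out to measure the prescriber proportion there. Record the invitation source, exclude enrichment invitees, and keep counting screened physicians after a quota closes. This must be in place before fielding, because under Section 3.4.4 reminders run only until the completion target is met.
- **Section 3.3.2 footnote and Section 8:** say that the no-bias expectation does not apply to an unweighted overall figure.
- **Section 7:** note that the simple-sample margins in Table 1 do not apply to the weighted estimate, with the ±6.3 example.

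The cost is wording, one recorded variable and continued screening counts. The stated margin for the overall estimate becomes wider. Weights taken from the screener describe those who respond, so they do not correct for self-selected non-response, and Section 8 should keep that limitation.
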